### 7.2.4 PAT Analysis

The RH-PAT data will be analyzed by a computer in an operator-independent manner. As a measure of the extent of reactive hyperemia, the RH-PAT index was calculated as the ratio of the average amplitude of the PAT signal over a 1-min time interval starting 1 min after cuff deflation divided by the average amplitude of the PAT signal of a 3.5-min time period before cuff inflation (baseline). RH-PAT index values from the study arm were then normalized to the control arm to compensate for potential systemic changes.

### 7.2.5 Calf Blood Flow in Reactive Hyperemia (CBF-RH)

Calf blood flow (CBF) will be determined using venous occlusion plethysmography and calibrated mercury strain-gauges (EC-6, D.E. Hokanson Inc., Bellevue, Washington, USA) during reactive hyperemia after a 5 min of ischemia of the distal limb. Strain-gauges will be applied to the widest part of the non-dominant calf (~10 cm below patella). Participants will remain quietly supine for 10 min with legs elevated on foam pads above the right atrium to achieve stable baseline measurements of CBF. The venous occlusion cuff is inflated for 4 seconds at

8 seconds intervals, while monitoring the change in resistance in the system, pressure inside the measuring cuff, and 5-10 determinations are performed. The plethysmograph output signal will be transmitted recorded using the WINDAQ data acquisition system (DI220, DATAQ, Akron, OH, 14 Bit, 500Hz) and processed off-line. The slope will be expressed as milliliters (ml) per minute per 100 ml of forearm tissue (ml/min/100 ml tissue). After 1 minute of ankle cuff inflation to 50 mm Hg above subject's systolic blood pressure to occlude ankle circulation, resting blood flow will be measured as the average of the last 4 of 5 plethysmographic measurements for 1 minute. Peak CBF will be then measured after 5 minutes of ischemia using a cuff inflated to 50 mm Hg above subject's systolic blood pressure, using a cuff located proximal to the patella. Again one minute before thigh cuff release, the ankle cuff will be inflated to 50 mm Hg above subject's systolic blood pressure, and measurements of CBF will be repeated for the next 3 minutes.

#### **7.2.6 Protein expression of harvested endothelial cells**

A 20-gauge intravenous catheter will be inserted into a superficial forearm vein. Under sterile conditions, 3 J-shaped vascular guidewires will be sequentially advanced into the vein up to 10 cm. Endothelial cells will be retrieved from the wire tips by washing with cell dissociation buffer (Invitrogen) at 4 °C. Endothelial cells will be recovered by centrifugation and fixed with 3.7% formaldehyde in PBS for 10 minutes, washed twice with PBS, transferred to poly-L-lysine coated slides (Sigma), and air dried at 37°C. The slides will be then stored at -70 °C until analyzed.

Using this procedure it is possible to measure basal eNO production and activity measuring venous endothelial expression of total eNOS and activated eNOS (P-eNOS) by quantitative immunofluorescence. Vascular inflammation and oxidative stress can be determined by measuring venous endothelial expression of nuclear factor-κB (NFκB) and nitrotyrosine.

#### **7.2.6 Evaluation of Forearm-Mediated Dilatation**

Subjects will be fasting for at least 2 hours prior to the study and will be instructed to avoid exercising the day before the study. All studies will be conducted in a quiet, temperature-controlled room. All subjects will rest in the supine position for at least 30 minutes after all instrumentation procedures are done. The arm will be kept extended and immobilized at heart level. Brachial artery diameter will be measured using a high resolution ultrasonography (iU22 xMatrix Ultrasound System, Philips, Andover MA) using a linear array probe with a 5 to 17 MHz frequency range (L17-5 Broadband Linear Array Transducer, Philips, Andover MA). The brachial artery will be imaged in longitudinal sections, 5-10 cm proximal to placement of an occlusion cuff in the dominant forearm just below the antecubital fossa. The probe will be held with a stereotaxic holder with micrometer movement capabilities.

When the clearest B-mode image through the center of the vessel is obtained with optimal contrast between the anterior and posterior vessel walls and the lumen of the vessel, the stereotaxic clamp will be fixed in place. Baseline diameter will be examined before cuff inflation for at least 1 minute. The rapid occlusion cuff (Hokanson) will be inflated and maintained for 5 minutes at 50 mm Hg above the subject's systolic blood pressure to produce transient ischemia. Measurement of post-deflation diameter will be initiated before cuff release and continue for 5 minutes following deflation.

Flow velocity and brachial artery diameter will be continuously measured using duplex ultrasound. Blood velocity will be assessed using an insonation angle <60°. The B-mode will

update synchronously with the R-wave of the ECG while also having a continuous Doppler spectrum recording throughout.

One experienced sonographer will collect all images. Images will be digitized from the video output of the ultrasound machine using a frame grabber on a personal computer. Image acquisition will be gated with an ECG signal so that images will be captured at end diastole at each cardiac cycle.

Brachial artery diameter will be assessed by a single trained operator using an automated, beat-by-beat edge detection and wall-tracking image processing software (Vascular Tools 5.0, Medical Imaging Applications, USA). Peak diameter will be calculated using automated mathematical algorithms. Data will be presented as absolute (mm) and relative FMD response (%). The area under the curve until peak diameter will also be measured and presented.

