### 7.3 Study Outcome Measures

- RH-PAT index
- Brachial artery diameter changes.
- CBF-RH
- Other blood parameters (outlined in section 7.2.1)

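### The plan does not mask the operator who reads FMD diameter (Aim 2, secondary) to diet phase; coding the image files would cheaply reduce, though not remove, a risk of reading bias of unknown size

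*Combined protocol and SAP*

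**What the plan says.** - **Blinding.** Section 6.3 answers in one word that there is none. It makes no exception for outcome reading.
- **Acquisition (Section 7.2.6 on forearm-mediated dilatation).** "One experienced sonographer will collect all images." The probe is clamped "When the clearest B-mode image through the center of the vessel is obtained". "Image acquisition will be gated with an ECG signal so that images will be captured at end diastole at each cardiac cycle." "Images will be digitized from the video output of the ultrasound machine using a frame grabber on a personal computer."
- **Reading (same section).** "Brachial artery diameter will be assessed by a single trained operator using an automated, beat-by-beat edge detection and wall-tracking image processing software." "Peak diameter will be calculated using automated mathematical algorithms." The section does not say whether the sonographer and this operator are the same person.
- **Reporting (same section).** "Data will be presented as absolute (mm) and relative FMD response" in per cent. The area under the diameter curve up to the peak is a third planned form.
- **Role of FMD.** Aim 2 (Section 4.2) asks whether FMD is lower on the high sodium diet. Section 7.3 lists "Brachial artery diameter changes" as an outcome, and Section 8.2 compares the Section 7.3 outcomes between diets with paired non-parametric tests. The primary outcome is the RH-PAT index (Section 8.1).
- **Related text.** Section 7.2.4 describes the RH-PAT analysis as computerised and operator-independent. Section 13.0 codes digital files to keep names and similar identifiers out. Section 2.2 commits FMD measurement to cited guidelines.

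**The concern.** Section 4.1 predicts that endothelial dysfunction will be worse on the high sodium diet. A reader who knows the diet phase therefore knows which way each test is expected to go. Pairing removes stable differences between subjects, and a reading habit that is the same on both diets. It does not remove a reading error that follows the diet. With one reader and no second reading planned, the data would not reveal such an error.

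What is at stake is the credibility of Aim 2. The diets cannot easily be hidden from subjects, but stored images can be hidden from the person who measures them, so this protection is available even in an open study.

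**Working it through.** **1. Is the reader masked anywhere?** Four places could supply masking.

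- Section 6.3 declares no blinding.
- The FMD section assigns the read to one operator and says nothing about what that person knows.
- Section 13.0 codes files for confidentiality. It does not mention diet phase or visit order.
- Section 2.2 refers to external guidelines. Whether they require masked reading cannot be seen from the documents.

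None of these masks the operator to diet phase.

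**2. Does automation close the gap?** The fixed holder, gated frames, edge detection and algorithmic peak all narrow the room for judgement. The plan still says that an operator assesses diameter, and it uses the term operator-independent only for RH-PAT. It describes no particular reader decision that would vary with diet. The risk is therefore limited but not excluded.

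**3. Which reading errors would matter?** Let B and P be the true baseline and peak diameters and e a reading error in mm.

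- *Same error in both images.* Absolute FMD is (P + e) − (B + e) = P − B, so the error cancels exactly. Relative FMD is 100(P − B)/(B + e), the true value multiplied by B/(B + e), so it nearly cancels when e is small against B.
- *Error in the peak only.* Absolute FMD shifts by e, and relative FMD by 100e/B.
- *Error in the baseline only.* Absolute FMD shifts by −e, and relative FMD by −100eP/[B(B + e)].
- *Area under the curve up to the peak.* If the area is taken above baseline, a common error cancels. If it is taken on raw diameter, a common error adds e times the time to peak. The plan does not say which is meant.

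The following numbers only check the algebra. True FMD of 6%, baselines of 3.00 and 5.00 mm and e = ±0.05 mm are all assumed; none comes from the documents. Entries are shifts in relative FMD, in percentage points, for a single test.

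| Error in | B = 3.00, P = 3.18: e = +0.05 / −0.05 | B = 5.00, P = 5.30: e = +0.05 / −0.05 |
|---|---|---|
| Both images | −0.098 / +0.102 | −0.059 / +0.061 |
| Peak only | +1.667 / −1.667 | +1.000 / −1.000 |
| Baseline only | −1.738 / +1.797 | −1.050 / +1.071 |

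For example, with the baseline alone read 0.05 mm too small at 3.00 mm: 100 × (3.18 − 2.95)/2.95 = 7.797%, a shift of +1.797. A single-test shift becomes a between-diet shift of the same size only if the error occurs on one diet and not on the other.

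For absolute FMD, and nearly so for relative FMD, an error biases Aim 2 only if it differs both between baseline and peak and between diets.

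**4. What cannot be computed.** The documents give no FMD reading error, no FMD effect size and no SD of the paired FMD difference. The planning figures in Section 8.3 concern RH-PAT alone. The main one reproduces: with effect size 0.25/0.5 = 0.5 and a two-sided 0.05 level, a paired t-test with 44 subjects has power 0.900. It says nothing about FMD, and masking the reader changes none of it.

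**The case against.** The strongest reply is that this is a declared design choice whose risk has largely been engineered out. The holder is fixed, frames are taken at a set point of the cardiac cycle, software tracks the wall beat by beat, and an algorithm finds the peak. No operator step open to diet-linked judgement is described. This lowers the weight of the point. It does not remove it, because the text gives the assessment to a person and does not claim independence from that person.

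Two further replies depend on matters the documents do not settle. The cited guidelines may already ask for masked reading; if so, Sections 2.2 and 6.3 need reconciling. Off-line reading is also inferred: the FMD section speaks of continuous measurement of diameter, although digitising images to a computer for processing software makes later reading likely.

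It is also fair to say that the same reasoning reaches other measures, such as the calf blood flow signals processed off-line under Section 7.2.5. An exception for FMD alone would imply that those should stay unmasked.

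A reader might infer more: that the FMD comparison will be biased, that its false-positive rate is inflated by some stated amount, or that the trial's main result is compromised. The documents support none of these. They show no biased reading step, they give no SD from which an error rate could be worked out, and the primary outcome is analysed without operator input.

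**Conclusion.** The point holds as a low-priority improvement. The plan leaves the FMD reader unmasked to diet phase, and nothing elsewhere in it fills the gap. The consequence is an unguarded risk of reading bias in one secondary outcome. No magnitude is claimed, and the assumed values in the table are not an estimate for this trial.

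The conclusion rests on the text as it stands, with two open matters: whether reading is done off-line from stored files, and whether the sonographer is also the reader. The primary analysis, sample size and power are unaffected.

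**What to change.** In Section 6.3, keep the statement that diet and image acquisition are unblinded, and add wording to this effect:

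> Digitised FMD files, with the baseline and post-deflation images of each test kept together, receive a random code that hides subject, diet phase and visit order. An existing staff member other than the reader holds the code. The same single operator reads the files in random order. Unmasking takes place only after the readings are locked. Other operator-processed off-line measures, such as the calf blood flow slopes, are coded in the same way where feasible.

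In the FMD section, cross-refer to this rule, confirm that reading is done off-line, and state whether the sonographer is also the reader. It would help to say there whether the area under the curve is measured above baseline.

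The cost is minor: file recoding as an extension of the coding in Section 13.0, and reading in batches instead of test by test. No extra reader and no extra procedure for subjects is needed. The change reduces the risk but does not remove it, because acquisition stays unmasked and masking is weaker if one person both acquires and reads the images.

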### 7.3 Study Outcome Measures

- RH-PAT index
- Brachial artery diameter changes.
- CBF-RH
- Other blood parameters (outlined in section 7.2.1)

## 8.0 STATISTICAL CONSIDERATIONS

### 8.1 Primary Analysis

The primary outcome measure will be the RH-PAT index. The primary analysis will involve a non-parametric, paired, Signed Rank test of RH-PAT between all subjects (POTS patients and control subjects) on the high sodium diet vs. the low sodium diet.

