## **6.0 ENROLLMENT, RANDOMIZATION & BLINDING**

### **6.1 Recruitment**

For the parent study, the patients with orthostatic intolerance will be recruited from patients referred to the Vanderbilt University Autonomic Dysfunction Center. Control subjects will be recruited from the Autonomic Research Database, the VICTR Research Participant Database, and advertising within the Vanderbilt Community. For this protocol, subjects enrolled in the parent study will be approached about this sub-study. Subjects will be assured that they are not required to participate in this study even if they choose to participate in the parent study.

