### **6.2 Randomization**

There will be no randomization for this specific sub-study. The order of diets (low sodium vs. high sodium) will be performed as a part of the parent study, and not as a part of this sub-study.

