### **7.2 Study Design**

The study will involve a crossover design in which each subject will be assessed (as below) while on a very low-sodium (10 mEq/day) diet compared with a very high-sodium diet. These acute dietary interventions will be part of the parent study ("Dietary Salt in Postural Tachycardia Syndrome" funded by R01 HL102387) for 4-5 days at the time of the study.

Dietary success will be assessed using a 24h urine for sodium and creatinine as a part of the parent study.

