### 8.2 Secondary Analysis

Secondary analyses will include non-parametric paired comparisons between low sodium and high sodium diets of continuous outcome measures (outlined in section 7.3). Secondary comparisons might also assess differences in the dietary sodium induced changes between POTS patients and control subjects.

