### 8.3 Sample Size Calculation

As this is a pilot study, there are no preliminary data available on the RH-PAT index in different sodium diets. Published data indicate that the RH-PAT index in 39 healthy subjects without endothelial function is  $1.78 \pm 0.08$  (mean  $\pm$  SEM). In the same study, RH-PAT  $< 1.35$  was found to be the best discriminator of coronary endothelial function. We will designate a more conservative  $\Delta$ RH-PAT = 0.25 as a clinically significant difference between high sodium diet vs. low sodium diet for the entire group. We expect the standard deviation around the difference will be 0.5 (based on the above data), for an effect size of 0.5. With the aforementioned assumptions for a paired test of continuous data, and a 0.05 two-sided significance level, a sample size of 44 (combined POTS patients and control subjects) would give 90% power to detect this difference. To account for drop-outs, we propose to enroll up to 50 subjects in total from the parent study. Using the same assumptions, 33 subjects would give 80% power to detect the same difference (in case of enrollment difficulties for this sub-study).

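### The crossover tests in 8.1 and 8.2 ignore diet order; a pre-stated period-adjusted rank test would be a cheap improvement

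*Combined protocol and SAP*

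**What the plan says.** Section 7.2 sets the design: "The study will involve a crossover design in which each subject will be assessed" on both diets. Section 6.2 states that the sub-study itself randomises nothing and that "The order of diets (low sodium vs. high sodium) will be performed as a part of the parent study". No sequence ratio is given. Section 6.1 makes participation optional: "Subjects will be assured that they are not required to participate in this study even if they choose to participate in the parent study".

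The primary analysis in 8.1 pools everyone: "The primary analysis will involve a non-parametric, paired, Signed Rank test of RH-PAT between all subjects (POTS patients and control subjects"), high against low sodium. Section 8.2 follows the same pattern: "Secondary analyses will include non-parametric paired comparisons between low sodium and high sodium diets of continuous outcome measures". It adds a possible group contrast: "Secondary comparisons might also assess differences in the dietary sodium induced changes between POTS patients and control subjects". No section mentions a period or sequence term, carry-over, or a count of subjects per diet order.

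Section 8.3 justifies 44 subjects for 90% power with a paired test (difference 0.25, SD of the differences 0.5, two-sided 5%), and adds that "33 subjects would give 80% power to detect the same difference (in case of enrollment difficulties for this sub-study").

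**The concern.** Each subject's RH-PAT is measured at two visits. If the index drifts between visits for reasons unrelated to diet, the drift adds to the high-minus-low difference in subjects who had low sodium first and subtracts from it in the others. The planned tests cannot tell this from a diet effect.

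With equal numbers per order the drift cancels in the estimate but widens the spread, which costs power. With unequal numbers it also biases the estimate, and power rises or falls with the direction of the drift. The same applies to the POTS-versus-control contrast if the two groups differ in their mix of orders.

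Because 6.2 mentions diet order under its randomisation heading, randomised order in the parent study is the natural reading. Even so, a voluntary subset need not keep the parent study's balance. Section 7.2.4 offers partial protection: "RH-PAT index values from the study arm were then normalized to the control arm to compensate for potential systemic changes". That may shrink a visit-to-visit shift but does not rule one out.

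**Working it through.** **The plan's own figures.** From 8.3: δ = 0.25, SD of differences 0.5, α = 0.05 two-sided. The normal formula n = [SD(z₀.₉₇₅ + z_power)/δ]² gives [0.5 × (1.960 + 1.282)/0.25]² = 42.0, so 43, for 90%, and [0.5 × (1.960 + 0.842)/0.25]² = 31.4, so 32, for 80%. The exact paired t-test has power 90.0% at n=44 and 79.5% at n=33. Both stated figures reproduce closely.

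**Model.** Let π be the shift from visit 1 to visit 2, n₁ the number low-first and n₂ the number high-first.

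- Mean high-minus-low difference: δ + π (low-first), δ − π (high-first).
- Pooled estimate: δ + π(n₁ − n₂)/n. At 28/16 and π = 0.25 the bias is 0.25 × 12/44 = 0.068; at 24/20 it is 0.25 × 4/44 = 0.023.
- Mean visit-2-minus-visit-1 difference: π + δ (low-first), π − δ (high-first). Their difference is 2δ, so π cancels whatever the split.

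**Assumptions.** The documents give neither π nor the split. I take π from 0 to 0.25 (the top value equals the target difference) and splits that 1:1 allocation can produce. Differences are normal with SD 0.5 around their sequence mean.

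**Fixed splits, n=44** (simulation, 100,000 trials per cell). SR is the planned signed-rank test; RS is the rank-sum test of period differences between orders. Each cell lists π = 0.10; 0.15; 0.25. Paired powers are for a favourable/unfavourable direction of the shift. The second column is the exact binomial chance, under 1:1, of a split this uneven or worse.

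| Split | Chance | Bias | SR type I % | SR power % | RS power % |
|---|---|---|---|---|---|
| 22/22 | – | 0 | 4.5; 4.0; 2.8 | 88; 87; 83 | 88 |
| 24/20 | 65% | 0.009; 0.014; 0.023 | 4.7; 4.4; 3.5 | 90/86; 90/83; 89/74 | 88 |
| 26/18 | 29% | 0.018; 0.027; 0.045 | 5.2; 5.4; 5.9 | 92/82; 93/78; 94/65 | 87 |
| 28/16 | 9.6% | 0.027; 0.041; 0.068 | 6.0; 7.0; 10.2 | 93/80; 95/73; 97/54 | 86 |

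RS type I error is about 5% throughout.

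**Averaged over 1:1 order** (200,000 trials), power in %, SR against RS:

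| π | n=44 | n=33 |
|---|---|---|
| 0 | 88.6 / 87.4 | 77.4 / 75.5 |
| 0.10 | 87.5 / 87.5 | 75.8 / 75.6 |
| 0.15 | 86.0 / 87.5 | 73.7 / 75.5 |
| 0.25 | 80.8 / 87.6 | 67.6 / 75.7 |

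Averaged type I error is 4.8 to 5.1% for both tests at every π. At n=33 with a 19/14 split (this or worse in 49% of draws) and π = 0.25, SR power is 82/53% against 76% for RS.

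**POTS against control.** Assume 22 per group, a true contrast of 0.4, and low-first/high-first counts of 13/9 and 9/13; low-first counts differ by 4 or more in 29% of 1:1 draws. The contrast moves by π × (4/22 + 4/22) = 0.364π, which is 0.036 at π = 0.10 and 0.091 at 0.25. Unadjusted type I error is 5.1% and 5.7%, and power 77/62% and 82/39%, against about 69% when stratified by sequence.

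**The case against.** A paired signed-rank test is a standard analysis of a two-period crossover, and under 1:1 order it holds its level on average. The study calls itself a pilot. Nothing in the documents points to a period shift, and averaged over 1:1 order the adjusted test loses power unless π exceeds about 0.10, which is 40% of the target difference. The striking figures need π as large as the diet effect and an uneven split, and the low powers also need the unfavourable direction. At 24/20 the planned test is conservative, not inflated. All of this stands, and it is why the point is an improvement and not an error.

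A second objection is that the simulation adds π on top of an SD of 0.5. If 0.5 already includes period variation, signed-rank power at 22/22 is about 89, 90 and 91% at π = 0.10, 0.15 and 0.25, so there is no shortfall from plan. This also stands, but the rank-sum test then gives about 89, 91 and 95%, so a gain remains.

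Third, the parent protocol is not available here and may specify balanced order. That would not guarantee balance among those who opt in, nor put a period term into 8.1. Fourth, the POTS-versus-control comparison is only a possibility in 8.2, and its group sizes and contrast above are assumed; those figures illustrate the mechanism only.

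Finally, changing the primary test touches the basis of 8.3. That is fair, and the fix covers it.

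**Conclusion.** The point holds as an inexpensive improvement, not a validity fault. The planned tests use no information on diet order. What adjustment buys is an estimate free of period bias given the split that actually occurs and, if π is above about 0.10, better average power: 1.5 points at π = 0.15 (86.0 to 87.5%) and 6.8 at π = 0.25 (80.8 to 87.6%) for n=44. For smaller shifts the planned test is equal or slightly better on average. Type I error is clearly inflated only at uneven splits, reaching 10.2% at 28/16 with π = 0.25. The sizes rest on assumed values of π and of the split, on normal differences, and on an SD of 0.5 that excludes the period shift. The absence of any period or sequence term rests on the text alone.

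**What to change.** Import each subject's diet order from the parent study and report subjects per sequence, overall and by POTS/control. Before outcome data are examined, state the rule below, based on the parent design and not on a test for a period effect.

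- **If both orders occur:** make the 8.1 test a Wilcoxon rank-sum comparison of visit-2-minus-visit-1 differences between sequences. Report half the Hodges-Lehmann shift (low-first minus high-first), with its 95% confidence limits halved, as the high-minus-low effect. Keep the signed-rank test as a sensitivity analysis. Use the same method for the diet comparisons in 8.2. For any POTS-versus-control comparison of diet-induced changes, stratify by sequence, for example with a van Elteren test.
- **If only one order was used:** keep the planned test and state that diet and period effects cannot be separated.
- **In either case:** align the test description and powers in 8.3 with the test actually used.

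State also that the adjusted estimate assumes no differential carry-over. Half of any such carry-over stays in it, as it does in the planned test at equal sequences.

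The cost is SAP wording and one existing variable; no subjects, visits or procedures are added. If there is no period shift, average power falls from 88.6 to 87.4% at n=44 and from 77.4 to 75.5% at n=33. By split at n=44 the loss is 0.4 points at 22/22, 0.9 at 24/20, 1.7 at 26/18 and 3.1 at 28/16; at n=33 it is 1 point at 19/14 and 5.6 at 22/11. Stratifying the group contrast costs about 1.5 points with equal splits (71.4 to 69.9%) and 2.6 at 13/9 against 9/13.
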